7.2 PARTICIPANT DISCONTINUATION/WITHDRAWAL FROM THE STUDY

Participants are free to withdraw from participation in the study at any time upon request.

An investigator may discontinue a participant from the study for the following reasons:

- Lost-to-follow up; unable to contact subject
- Participant withdraws consent for further participation and/or data use.
- Participant texts “STOP” to the experimental intervention phone number.
- Safety concerns: any SAE or AE judged related to participation that warrants removal, per the Data and Safety Monitoring Plan and IRB reporting rules.
- Ineligibility discovered post-enrollment, duplicate enrollment, or other protocol violations that compromise data integrity.
- Investigator decision that continued participation poses undue burden or risk (e.g., credible threats of harm), consistent with IRB policies.

The reason for participant discontinuation or withdrawal from the study will be recorded on a dedicated Case Report Form (CRF). Participants who withdraw or are discontinued after randomization will not be replaced; enrollment continues until the target sample size is reached.

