9.2 SAMPLE SIZE DETERMINATION

To determine the adequate sample size for our study, we examined achieved power and treatment effects for a study examining the efficacy of a conceptually similar intervention with an equivalent data analysis plan. Specifically, Miller et al. developed a digital decision aid to help patients select a CRC screening test before a primary care appointment. Compared to controls, participants assigned to the decision aid were twice as likely to get screened at 6-month followup (30% [67/223] vs. 15% [34/227], difference=15%, 95% CI 7% to 23%; OR = 2.5). Follow-up analyses with only nonwhite participants continued to show a significant positive effect on screening (34% [33/98] vs. 19% [18/94], difference = 15%, 95% CI 6% to 25%; OR=1.79). Based on the similarity of this research to our own, we anticipate similar screening proportions in our study. To estimate power for the binomial logistic regression analysis on the primary outcome measure (MRR-verified CRC screening), we relied on the sub-analysis from Miller et al.'s data. Importantly, the OR in this analysis (1.79) is consistent with the average effect size of SMS-based interventions on health behaviors (OR=1.81). The G*Power 3.1 program was used to

determine that an odds ratio of 1.79, a two-tailed α error probability of 0.05, and 80% power requires a final sample size of 154 to detect an expected difference in screening rates of 15% at the 6-month follow-up. While unlikely, we will anticipate a conservative 20% attrition rate and set our sample size at 193 (n= 154 post-attrition).

As screening-related health beliefs are important secondary outcomes, we also examined power using treatment effects for screening self-efficacy from the Miller et al. decision aid study. Researchers found that participants in the intervention group reported significantly higher screening self-efficacy (n=223, M=3.89, SD=.84) than control participants (n=227, M=3.64, SD=1.00), $p=.004$. This difference is associated with a Cohen's $d = .27$. To detect a difference of this size in screening self-efficacy, our study will require a final sample size of 110 participants ($\alpha = 0.05$ two-tailed; power = .80). The 154 participants remaining in the analyses post-attrition will be sufficient to detect differences health beliefs across the two survey time points.

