10.1.2 STUDY DISCONTINUATION AND CLOSURE

This study may be temporarily suspended or prematurely terminated if there is sufficient reasonable cause. If the study is prematurely terminated or suspended, the Principal Investigator (PI) will promptly inform study participants, the Institutional Review Board (IRB), and sponsor/funding agency and will provide the reason(s) for the termination or suspension. Study participants will be contacted, as applicable, and be informed of changes to study appointment schedule.

Circumstances that may warrant termination or suspension include, but are not limited to:

- Determination of unexpected, significant, or unacceptable risk to participants
- Insufficient compliance of study staff to the protocol (ie, significant protocol violations)
- Determination that the primary endpoint has been met
- Determination of futility

The study may resume once concerns about safety, protocol compliance, and data quality are addressed, and satisfy the funding agency, sponsor, IRB, , or other relevant regulatory or oversight bodies (OHRP).

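### Section 9.2 plans 193 randomised (154 after attrition), the schema in 1.2 shows 128, and no visible text explains the difference or restates the power

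*Combined protocol and SAP*

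**What the plan says.** Three sections of the combined protocol and SAP bear on the size of the trial.

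- **9.2 (sample size).** The calculation assumes "a two-tailed α error probability of 0.05, and 80% power", takes its rates from a subgroup of a cited decision-aid trial ("34% [33/98] vs. 19% [18/94"), and concludes that the design "requires a final sample size of 154 to detect an expected difference in screening rates of 15% at the 6-month follow-up". It then adds an allowance ("we will anticipate a conservative 20% attrition rate") and arrives at "set our sample size at 193 (n= 154 post-attrition". It also states that 110 participants are needed for self-efficacy and that the 154 remaining will suffice for the health-belief outcomes.
- **7.2 (withdrawal).** Participants lost after randomisation "will not be replaced; enrollment continues until the target sample size is reached".
- **1.2 (schema).** The total is 128, with 63 in the experimental arm and 65 in the control arm below the randomisation step.

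Section 10.1.2 allows premature termination for reasonable cause. Its open-ended list includes the primary endpoint having been met and "Determination of futility". Section 9.4.6 marks planned interim analyses as not applicable. The amendment history in 10.4 reads n/a in every cell.

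**The concern.** The planned number and the number in the schema cannot both describe the trial, and attrition does not bridge them, because 128 is below even the post-attrition figure. Two things follow.

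First, the size, the attrition allowance and the power in 9.2 are not those of the trial shown in 1.2. A reader who takes 80% power at face value will misjudge what a null result means.

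Second, the documents do not say why enrolment ended where it did. Section 10.1.2 lists outcome-related grounds for closure, and 9.4.6 provides no boundary to govern a look at the data. Section 6.3 says staff are not blinded, and 6.4 says experimental-arm reports of screening are logged as they arrive by text message. If enrolment ended because the endpoint looked to be met, the single 0.05 test would be affected. A stop for futility alone would not inflate type I error, though it would still matter for estimation.

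**Working it through.** **1. The plan's own target.** Inputs from 9.2: 154 analysable, 20% attrition. 154 / (1 − 0.20) = 192.5, rounded up to 193. The target reproduces.

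**2. The schema.** 63 + 65 = 128. The total is printed beside the pre-screening box, but the arm counts sum to it, so it is the randomised total.
- Against the target: 193 − 128 = 65 fewer; 128/193 = 66%.
- Against the post-attrition number: 154 − 128 = 26 fewer; 128/154 = 83%.

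**3. Power for 34% against 19%.** Two-proportion z test, two-sided 0.05:

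power = Φ[(d − 1.96·SE0) / SE1], with d = 0.15, SE0 = √[p̄(1 − p̄)(1/n1 + 1/n2)] and SE1 = √[p1(1 − p1)/n1 + p2(1 − p2)/n2].

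At 63/65: p̄ = 0.264, SE0 = 0.0779, SE1 = 0.0770, so (0.15 − 0.1527)/0.0770 = −0.035 and Φ = 0.486.

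| Analysed | Power |
|---|---|
| 193 | 65.8% |
| 154 (77/77) | 56.0% |
| 128 (63/65) | 48.6% |
| about 102 (20% attrition from 128) | 40.5% |

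With the exact fractions 33/98 and 18/94, power at 63/65 is 46.2%.

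**4. Separating the shortfall from the formula.** The gap from the stated 80% is 80 − 48.6 = 31.4 points.
- Against 154: 56.0 − 48.6 = 7.4 points come from the shortfall, and 24.0 remain.
- Against 193 with every chart reviewed: 65.8 − 48.6 = 17.2 points come from the shortfall, and 14.2 remain.
- With 20% attrition applied to both sizes: 56.0 − 40.5 = 15.5 points come from the shortfall.

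The remainder arises because 154 is too small for this two-arm contrast at any stage: the same test needs 270 in total for 80% power. A logistic formula for a continuous, standard-normal predictor, with event rate 0.19 and odds ratio 1.79, gives (1.960 + 0.842)² / [0.19 × 0.81 × (ln 1.79)²] = 150.5, within 3% of 154. On that scale power is 80.9% at 154, 73.4% at 128 and 63.6% at 102, so the shortfall lowers power there too.

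**5. Sensitivity to the effect size.** Section 9.2 says "the OR in this analysis (1.79) is consistent with the average effect size of SMS-based interventions", but 34% against 19% is an odds ratio of (0.34/0.66)/(0.19/0.81) = 2.20. Taking 1.79 literally from a 19% control rate gives 29.6% in the intervention arm. Power is then 28.5% at 63/65, 33.2% at 154 and 40.1% at 193.

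**6. Detectable difference at 63/65.** Solving the step 3 formula for 80% power with a 19% control rate gives about 41.5% in the intervention arm, a gap of about 22 points against the planned 15.

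**7. Secondary endpoints.** 128 × 0.80 = 102.4, so about 102 follow-up surveys. That is 52 below 154 and 8 below the 110 that 9.2 states for self-efficacy. The 110 is taken as stated and is not verified here.

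**The case against.** The strongest reply is that 7.2 is not the only provision on ending enrolment. Its sentence closes a paragraph about replacing withdrawals, and 10.1.2 separately allows the study to stop early on grounds that are not limited to those listed. A reader might infer from 7.2 and 1.2 that the enrolment rule was broken. The documents do not support that: an early stop under 10.1.2 that was simply not reported fits them equally well.

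A reader might also infer that no amendment was made. Section 10.4 does read n/a, but it places the current summary of changes on the title page, which is not in the copy reviewed. Only the empty history table can be cited.

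A third tempting inference is that enrolment stopped on outcome data. Nothing says that anyone compared the arms, the closure grounds in 10.1.2 are generic, and 9.4.6 plans no interim analysis. The point is limited to the reason being unstated.

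It is also fair to say that 20% attrition is described in 9.2 as unlikely, that 9.3 expects very little missing data on the chart-based primary outcome, and that imputation is planned for the surveys. The 102 is therefore a consequence of the plan's own cautious assumption, not a forecast. And 128 might be a count taken before enrolment closed, although the past-tense account of conduct in 2.1 and 4.1 makes that unlikely.

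What survives all of this is the conflict between 1.2 and 9.2, with nothing visible to reconcile them.

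**Conclusion.** The point holds as an undocumented discrepancy: 193 planned, 128 shown, and a stated power that does not belong to the trial in the schema. At 63/65 the power for the plan's own rates is about 49%. It would be wrong to set 49% against 80% and attribute the whole difference to the shortfall, because meeting the target would have given only about 66% on the same test. How much belongs to the formula error depends on whether 154 or 193 is the comparator.

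These figures assume that 128 is the final randomised number, that charts are obtained for all 128, and that 34% and 19% are the relevant rates. The conflict in the counts needs none of the power assumptions.

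**What to change.** - **Keep the plan as planned.** Conduct is already reported in the past tense, so leave the 193 rationale in 9.2 and the wording of 7.2 in place; rewriting them would erase the original intention.
- **Add a dated note** reconciling 1.2, 7.2 and 9.2, with an entry in 10.4. It should give the actual number randomised, the date and reason enrolment ended, and whether anyone had seen outcomes by arm at that time. The word is whether: the documents do not establish the answer.
- **Restate 9.2 at 63 against 65:** about 49% power for 34% against 19%; about 41.5% needed in the intervention arm for 80% power from a 19% control rate; and the expected number of follow-up surveys (about 102 at the plan's 20% attrition). Label these as describing the achieved size, separate from any correction of the original formula.

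The cost is text only. The downside is a less favourable stated power. No additional enrolment is proposed.

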7.3 LOST TO FOLLOW-UP

A participant will be considered lost to follow-up if he or she fails to respond for the 6-month follow-up call and study staff are unable to contact the participant after at least 3 attempts.

The following actions must be taken if a participant fails to respond for a required study appointment:

- The site will attempt to contact the participant, reschedule the missed baseline or follow-up appointment, counsel the participant on the importance of maintaining the assigned visit schedule and ascertain if the participant wishes to and/or should continue in the study
- Before a participant is deemed lost to follow-up, the investigator or designee will make every effort to regain contact with the participant (where possible, 3 telephone calls including to a secondary contact number). These contact attempts will be documented in the participant’s study file.
- Should the participant continue to be unreachable, he or she will be considered to have withdrawn from the study with a primary reason of lost to follow-up.

8 STUDY ASSESSMENTS AND PROCEDURES

No text is to be entered in this section; rather it should be included under the relevant subheadings below.

8.1 ENDPOINT AND OTHER NON-SAFETY ASSESSMENTS

This individually randomized, remote trial evaluates a mobile, video+SMS colorectal cancer (CRC) screening education program versus a standard-materials control. All study activities are conducted virtually; no study-specific physical exams, imaging, or biospecimen collection occur. Outcome verification uses medical record review (MRR) and self-report.

Screening, eligibility, and enrollment

- **Eligibility confirmation window.** Up to 30 days prior to enrollment. Site staff confirm basic eligibility from clinic records (e.g., age, overdue for CRC screening per guidelines, active phone number).
- **Consent & MRR authorization.** Participants complete electronic informed consent and provide HIPAA authorization for MRR.
- **Baseline survey.** Immediately post-consent, participants complete a baseline questionnaire.
- **Randomization.** After baseline completion, participants are assigned to intervention or control.

Interventions begin (initial administration conditions)

- **Intervention arm.** Participants receive an SMS link to the curriculum hub and proceed through brief, pre-recorded videos with tailored branches, followed by a post-education screening assistance (PESA) text sequence.
- **Control arm.** Participants receive text messages, some with links to standard educational materials via SMS. A working mobile number and ability to receive texts are required for delivery; there are no in-person or group sessions.

Measures and assessments (non-safety)

Baseline (pre-randomization)

- Demographics and contact details (mobile number required for delivery).
- CRC screening history (ever screened; modality and timing if applicable).
- Psychosocial measures (e.g., CRC knowledge; perceived risk/severity; perceived benefits/barriers for stool tests and colonoscopy; medical trust; self-efficacy).

During intervention (process/dose)

- Platform telemetry: timestamps for each SMS, link launches, chapter/video opens (percent viewed), assessment completions, participant replies (including keyword confirmations), and time in the assistance stream. These are used for exposure/dose summaries and adherence monitoring (not safety).

Follow-up (primary outcome window)

- **Primary outcome ascertainment:** Receipt of any guideline-concordant CRC screening within 6 months post-randomization, verified by MRR (test type, date, and result if available) and self-report.
- **Follow-up questionnaire:** repeat of key psychosocial measures to explore mechanisms and acceptability.

Outcome definitions (non-safety)

- **CRC screening completion:** Documentation in the medical record or self-report of colonoscopy, FIT, FIT-DNA, CT colonography, or flexible sigmoidoscopy performed within the 6-month window (plus any pre-specified grace period).

- **Exposure/dose metrics:** Number of SMS delivered; proportion eliciting a response; number/proportion of videos opened by chapter; completion of the immediate post-education questionnaire; and elapsed days in PESA until closeout.

Administration, scoring, and data quality

- **Administration.** All questionnaires are administered via telephone.
- **Scoring.** Multi-item scales are scored per codebook (sum or mean of valid items; higher scores reflect greater endorsement or knowledge, as defined). Missing-data rules (e.g., minimum items required) are pre-specified.
- **Data capture.** Survey responses and SMS telemetry are time-stamped and stored on the study platform; MRR uses standardized abstraction forms with dual review and reconciliation.

Qualified personnel

- **MRR:** Conducted by trained study staff (e.g., clinic research coordinators) using a standardized abstraction guide; complex clinical ambiguities are adjudicated by a qualified clinician (e.g., physician or advanced practice provider).
- **Telephone-based assessment:** Conducted by trained study staff.

Use of existing clinical data and HIPAA

The study uses existing medical charts to verify CRC screening. HIPAA, applicable federal/state laws, and local institutional requirements are followed. MRR variables include test type and date (and result if available). No central lab is used; no CLIA-covered testing is performed by the study.

Standard of care procedures

All screening tests are ordered and performed as part of routine clinical care, independent of the research team. The study does not alter clinical pathways, rescue therapy, or provider decision-making.

Results returned to participants

Participants receive general educational messages and resource links through the intervention or control SMS sequences. The study does not generate new clinical test results; any clinical results (e.g., from a colonoscopy) are communicated by the healthcare system per usual care.

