1 PROTOCOL SUMMARY

1.1 SYNOPSIS

Title:	Reducing Colorectal Cancer Health Disparities: An mHealth Intervention to Improve Screening among African American Men
Grant Number:	R44CA246899
Study Description:	Two-arm, parallel-group randomized controlled trial comparing a tailored, SMS-delivered mobile education program with attention-control (CDC video links) to improve completion of any guideline-concordant colorectal cancer (CRC) screening by ~6 months among Black/African American men who are non-adherent to CRC screening.
Objectives*:	Objectives: Primary—evaluate effect on completion of any guideline-concordant CRC screening since enrollment. Secondary—evaluate effects on CRC beliefs (severity, susceptibility, benefits/barriers), knowledge, self-efficacy, and medical trust.
Endpoints*:	Endpoints: Primary—binary indicator of any CRC screening since enrollment assessed at follow-up. Secondary—validated scale scores at baseline and follow-up.
Study Population:	Black/African American men who are aged 45–75, non-adherent to CRC screening, and smartphone owners in Washington, DC
Phase* or Stage:	Phase II clinical trial
Description of Sites/Facilities Enrolling Participants:	Single U.S. community health center in Washington, DC
Description of Study Intervention/Experimental Manipulation:	The study intervention includes a structured series of text messages that deliver links to brief, mobile-friendly videos on colorectal cancer risk, guideline-recommended screening options (FIT/FOBT, FIT-DNA, colonoscopy, CT colonography, and flexible sigmoidoscopy), and strategies to overcome common barriers. Messages are automated and paced over approximately 6–9 weeks, resulting in an estimated total exposure of about two hours of content. Comparator: CDC-developed CRC education links delivered by SMS and paced over 6 weeks. Estimated video length is 30–40 minutes total.
Study Duration*:	18 months
Participant Duration:	6 months

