2.2 BACKGROUND

CRC Screening Saves Lives

Most CRCs develop from precancerous polyps. Because these polyps grow slowly, early detection and removal can prevent the majority of cases from becoming invasive cancer.^{2,9,10} For average risk adults, the US Preventive Services Task Force (USPSTF) recommends regular screening between 50 and

75.³³ Several tests are approved to detect CRC or precancerous polyps. The “gold standard” is colonoscopy, a direct visualization of the colon and rectum.² This is the only procedure that allows for simultaneous detection and removal of polyps throughout the entire colon and rectum. It also requires retesting only every 10 years.^{2,34} Despite these advantages, significant barriers associated with colonoscopy include availability, cost, transportation, and the need to fully cleanse the colon with laxatives prior to testing.² As a result, stool-based screening methods, like the guaiac fecal occult blood test (gFOBT) and fecal immunochemical test (FIT), are popular alternatives.^{2,35,36} Both detect blood from CRC in stool but require annual rescreening. A newer fecal test, FIT-DNA, can detect either blood or genetic mutations shed by CRC and polyps and is recommended every 1-3 years.² Irrespective of which fecal test is performed, any positive result should be followed by colonoscopy.² Ultimately, most medical and research professionals agree that “the best test is the one that gets done.”³⁷

CRC Screening in African American Men

Unfortunately, adherence to any of these CRC screening options is far too low. This is especially true among men, particularly those who are younger and low SES.^{38,39} Given this, it is not surprising that screening compliance is particularly poor among low SES African American men.^{2,11}

Socioeconomic disadvantage in the United States is associated with lower colorectal cancer screening rates.¹²⁻¹⁵ Contributing factors include inconsistent health insurance,^{40,41} out-of-pocket costs for CRC screening tests,^{40,42} and few interactions with primary care.⁴³ In clinical settings, some patients report receiving less comprehensive counseling about screening and fewer screening recommendations,^{40,41,44} as well as feeling unheard or treated impersonally.⁴⁵ Clinicians may also be less aware of practical barriers faced by patients with fewer resources^{46,47} and expectations about patient dependence or follow-through can vary by socioeconomic context.⁴⁸

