9.1 STATISTICAL HYPOTHESES

- Primary Endpoint(s):

We hypothesize that, compared to participants who receive standard educational materials via SMS (control), participants who receive the tailored mobile video+SMS intervention (m-CRCSi) will have a higher proportion completing any guideline-concordant colorectal cancer (CRC) screening within 6 months post-randomization. Alternatively, our null hypothesis is that there will be no difference between arms in screening completion at 6 months.

- Secondary Endpoint(s):

Self-reported proxy screening composite (6 months):

We hypothesize that the intervention arm will report a higher rate of any guideline-concordant CRC screening by 6 months than the control arm; the null hypothesis is that there will be no difference between arms.

CRC knowledge (baseline→6 months):

We hypothesize that intervention participants will show greater improvement in CRC knowledge from baseline to 6 months than control participants; the null hypothesis is that there will be no difference in change between arms.

Perceived susceptibility and severity (baseline→6 months):

We hypothesize that intervention participants will report greater increases in perceived susceptibility and severity from baseline to 6 months than control participants; the null hypothesis is that there will be no difference in change between arms.

Perceived benefits and barriers for colonoscopy and stool testing (baseline→6 months):

We hypothesize that intervention participants will report greater increases in perceived benefits and greater decreases in perceived barriers from baseline to 6 months than control participants; the null hypothesis is that there will be no difference in change between arms.

Medical trust (baseline→6 months):

We hypothesize that intervention participants will report greater increases in trust in the medical profession from baseline to 6 months than control participants; the null hypothesis is that there will be no difference in change between arms.

Self-efficacy (overall; colonoscopy; stool test) and advocacy (baseline→6 months):

We hypothesize that intervention participants will demonstrate greater improvements from baseline to 6 months than control participants; the null hypothesis is that there will be no difference in change between arms.

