10.1.1.2 CONSENT PROCEDURES AND DOCUMENTATION

The field test coordinator will provide eligible men with a detailed overview of the main points of the study. First, participants will be reminded that, although health information of a sensitive nature will be included in the intervention or control materials and the survey, their names will not be associated with their survey responses or their assigned materials. The field test coordinator will also explain the flow of the study procedures and what will be asked of participants. Participants will be told that the two surveys – the baseline survey and a follow-up survey six months later – will take approximately one hour to complete. They will also be informed that their medical records will be checked again at the end of the study to verify whether they received CRC screening since the study began. Further, men will be told that half of the participants will be asked to go through the m-CRCSi after the first survey while the other half will review CRC materials developed by the CDC via a link texted to their study phone number. Those who do not go through the m-CRCSi will be given access to it after the second survey. All participants will be informed that they will complete the research surveys via telephone with the study coordinator reading the questions and recording participant responses. They will also be told that their assigned materials can all be reviewed remotely on their smartphones. Procedures for mobile phone safety will be reviewed. Finally, the field test coordinator will also explain that participants will receive \$75 for completing the baseline survey and \$100 for completing the 6-month follow-up survey. Once any participant questions are answered, eligible men will be sent a text message linking to the informed consent form. Next, the potential participant will review the informed consent document. The ISA staff member will remain on the phone while potential participants review the informed consent and will encourage them to ask any questions they may have about the study.

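### The Section 8.1 outcome definition omits FOBT/gFOBT, which the synopsis lists as guideline-recommended, and it allows a grace period that no section specifies

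*Combined protocol and SAP*

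**What the plan says.** **Test list.** The outcome definition in Section 8.1 accepts a medical record entry or self-report of "colonoscopy, FIT, FIT-DNA, CT colonography, or flexible sigmoidoscopy performed within the 6-month window (plus any pre-specified grace period"). It has no 'such as' or 'other' category. The synopsis (1.1) describes the intervention as teaching "guideline-recommended screening options (FIT/FOBT, FIT-DNA, colonoscopy, CT colonography, and flexible sigmoidoscopy"). Section 2.2 names two distinct tests: "stool-based screening methods, like the guaiac fecal occult blood test (gFOBT) and fecal immunochemical test (FIT), are popular alternatives".

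**Endpoint in words.** The ascertainment bullet in Section 8.1 reads "Receipt of any guideline-concordant CRC screening within 6 months post-randomization, verified by MRR" and self-report. The primary hypothesis in Section 9.1 speaks of "completing any guideline-concordant colorectal cancer (CRC) screening within 6 months post-randomization". Both are open as to test type, and neither has a grace period.

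**Window.** Only the outcome definition in Section 8.1 mentions a grace period. The objectives table in Section 3 counts screening from study entry with no closing date. Section 10.1.1.2 tells men that their records will be checked at the end of the study for screening since it began, again with no closing date.

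**Control access.** Section 10.1.1.2 also says: "Those who do not go through the m-CRCSi will be given access to it after the second survey". That survey is planned for about Day 180 (1.2, 1.3).

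**The concern.** The sentence that turns the primary endpoint into a yes/no code disagrees with the sections that state the endpoint in words. A man who completes gFOBT meets the endpoint under Section 9.1 and the ascertainment bullet, but fails it under the definition. The intervention teaches FOBT as an acceptable choice and helps men pick a test that suits them (6.1.1), so choice of test may differ by arm. The outcome could then partly reflect which stool test was used rather than whether a man was screened.

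The window matters less but has the same character. A period described as pre-specified, with no value given anywhere, leaves the closing date of the primary outcome open. Time after the second survey is not like for like, because control men may by then have the experimental program.

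**Working it through.** No figure in the plan is in dispute. The check is a comparison of texts, followed by arithmetic for scale.

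**Step 1: is the conflict real?**

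| Place | Tests counted | Window |
|---|---|---|
| 1.1 Synopsis | any guideline-concordant; FIT/FOBT named | about 6 months, since enrollment |
| 3 Objectives table | CRC screening | since study entry, no close |
| 8.1 Ascertainment bullet | any guideline-concordant | 6 months |
| 8.1 Outcome definition | closed list, no FOBT | 6 months plus any grace period |
| 9.1 Primary hypothesis | any guideline-concordant | 6 months |
| 10.1.1.2 Consent | CRC screening | since the study began, no close |

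FOBT cannot be read as a synonym for FIT, because Section 2.2 separates them. The conflict is real.

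**Step 2: effect of leaving gFOBT uncounted.** The planning rates in Section 9.2 are 34% and 19%, a difference of 15 points. Let gE and gC be the gFOBT shares of completed tests in the experimental and control arms. Neither is in the documents, so all values below are assumptions. The observed difference is

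34(1 − gE) − 19(1 − gC) = 15 − 34gE + 19gC points.

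Power uses the two-sided 5% two-proportion normal approximation, Φ[(d − 1.96·SE0)/SE1], with SE0 pooled and SE1 unpooled. It is shown for the 63 and 65 men in the Section 1.2 schema and for 77 per arm (154/2, Section 9.2).

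Equal shares in both arms:

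| Share | Rates (%) | Difference (points) | Power, 63 vs 65 | Power, 77 per arm |
|---|---|---|---|---|
| 0% | 34.0 vs 19.0 | 15.0 | 48.6% | 56.0% |
| 5% | 32.3 vs 18.0 | 14.3 | 46.0% | 53.1% |
| 10% | 30.6 vs 17.1 | 13.5 | 43.4% | 50.2% |
| 20% | 27.2 vs 15.2 | 12.0 | 38.3% | 44.4% |
| 30% | 23.8 vs 13.3 | 10.5 | 33.3% | 38.7% |

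In men: 0.34 × 63 = 21.4 and 0.19 × 65 = 12.4 expected screens. Shares of 5% to 30% would miscode about 1 to 6 experimental and 1 to 4 control men.

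Unequal shares:

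- gE = 10%, gC = 0: 30.6 − 19.0 = 11.6 points.
- gE = 20%, gC = 0: 27.2 − 19.0 = 8.2 points.
- gE = 10%, gC = 30%: 30.6 − 13.3 = 17.3 points.

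The difference shrinks when 34gE exceeds 19gC, and widens when gC is more than 34/19 = 1.79 times gE. The direction is therefore not determined.

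**Step 3: effect of a grace period, if one were used.** Assume that it adds a net 1, 2, 4 or 6 points of control-arm tests after access. The difference becomes 14, 13, 11 or 9 points, and power at 63 vs 65 becomes 43%, 38%, 28% or 20%. With no grace period, this effect is zero.

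**The case against.** The case against runs as follows. The governing endpoint is any guideline-concordant screening. Section 8.1 also provides a standardized abstraction guide, dual review with reconciliation and clinician adjudication of ambiguities, and it records test type and date, so a gFOBT could be recognized or recoded later. If the clinic rarely uses gFOBT, the effect is trivial: at a 5% share the loss is under 3 power points. Part of this stands. The share is unknown and may be small, and recoding is possible provided that gFOBT results are abstracted. But dual review resolves disagreement between abstractors and does not correct a list that both apply faithfully. A test absent from the list is not evidently a complex clinical ambiguity.

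On the window, the text says any grace period, so there may be none. Control access follows the second survey, not a fixed day, so a man surveyed late also gets access late. The curriculum takes about 6 to 9 weeks (1.1), so a short grace period would catch few tests prompted by it. Self-report is collected at the second survey, before access, which leaves record review as the exposed route. All of this stands.

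A reader might infer three stronger things that the documents do not support:

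- **That men could be misclassified by arm.** Assignment is fixed by randomization and the analysis is intention-to-treat (9.3). The risk is contamination of control-arm outcomes.
- **That any grace day counts tests done after control access.** The overlap is only conditional, for the reasons just given.
- **That omitting FOBT must shrink the effect.** That requires similar shares by arm, or at least gC below 1.79 times gE.

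**Conclusion.** The point holds as an internal inconsistency in the definition of the primary outcome. Applied literally, the Section 8.1 list counts a gFOBT-screened man as unscreened, against the synopsis, Section 2.2, the ascertainment bullet and Section 9.1. Under equal assumed shares of 5% to 30%, the planning difference falls from 15 to between 14.3 and 10.5 points. Unequal shares could move it either way. The power figures are for scale only: the low starting value of about 49% reflects the schema counts and the planning rates, which is a separate matter.

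The undefined grace period is secondary and mostly missing detail. It could let record review pick up control-arm tests done after access to m-CRCSi, but the documents do not say that it will. The correction should be made because it concerns the primary endpoint and costs almost nothing, not because a large bias has been shown.

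**What to change.** 1. Add FOBT/gFOBT to the outcome definition in Section 8.1 and to the abstraction form, so that both match the synopsis.
2. Delete the grace-period clause. State the window as 6 months post-randomization in Section 3, both places in Section 8.1, Section 9.1 and Section 10.1.1.2. Apply it by date of test, identically in both arms, to record-review and self-reported tests alike. This leaves the self-report route as it is. Whether self-report belongs in the primary outcome is a separate question.

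**Cost.** One addition to a list, one form entry and aligned wording in four sections. Section 8.1 already collects test type and date from the record. The follow-up interview needs a test date as well, which is one item if it is not already asked. A few tests done just after the cutoff will not be counted. A fixed, stated grace period could also be made consistent, but it would have to be kept clear of control access, and a plain 6-month cutoff is simpler.

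**Timing.** Make and date the change without reference to results by arm. If abstraction is already done, recode from the recorded test types. If gFOBT was not captured, the charts need a second look before the linking file is deleted (10.1.3), since going back afterwards may not be possible.
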